1.0 DOCUMENT HISTORY

Version	Date	Changes made since previous version
0.01	27 Jan, 2016	First draft
1.00	20 October, 2016	Final after receiving FDA's comments dated on 01 Sept 2016
1.01	4 November, 2016	Due to differences in analyses requested by the FDA and EMA and to avoid confusion, as stated in the protocol, two SAPs will be prepared, one for FDA submission and one for the EMA submission. Additionally, this version incorporates FDA's comments dated on 04 Nov 2016. Version 1.00 was revised to reflect statistical analysis plan for the US FDA submission. The EMA specific variables are removed from Version 1.00. No analysis methodologies are changed from Version 1.00.

2.0 LIST OF ABBREVIATIONS

Abbreviation	Definition
AE	Adverse Event
ANCOVA	Analysis of Covariance
ANOVA	Analysis of Variance
BMI	Body Mass Index
BPN	Buprenorphine or Buprenorphine/Naloxone
CDF	Cumulative Distribution Function
COWS	Clinical Opiate Withdrawal Scale
CRF	Case Report Form (may include electronic data capture systems or paper forms)
FID	First Injection Date
ICH	International Council for Harmonisation
ITT	Intent-to-Treat
LD	Last Date in the study
LOCF	Last Observation Carried Forward
MedDRA	Medical Dictionary for Regulatory Activities
mg	Milligram
mITT	Modified Intent-to-Treat
PT	MedDRA Preferred Term
RR	Response Rate
SAE	Serious Adverse Event
SAP	Statistical Analysis Plan
SC	Subcutaneous
SD	Standard Deviation
SL	Sublingual
SOC	MedDRA System Organ Class
SOWS	Subjective Opiate Withdrawal Scale
TEAE	Treatment-Emergent Adverse Event
VAS	Visual Analog Scale

3.0 INTRODUCTION

This statistical analysis plan (SAP) is based on Protocol HS-11-421 Amendment 5, dated on November 3, 2016.

The purpose of this document is to provide details on study populations and on how the variables will be derived, how missing data will be handled, as well as details on statistical methodologies to be used to analyze the safety and efficacy data from the study.

The document may evolve over time, for example, to reflect the requirements of protocol amendments or regulatory requests. However, the final SAP must be finalized, approved by the Sponsor, and placed on file before database is locked and treatment codes are unblinded. Deviations from the approved plan will be noted in the clinical study report.

The primary endpoint response rate will be used to address the regulatory requirements as outlined by the US Food and Drug Administration (FDA). Specifically, the FDA requested an alternative primary efficacy responder definition on September 1, 2016, which have been incorporated in this final SAP. Additionally, the FDA provided comments on November 4, 2016 and recommended a NI margin of 10% points to be reasonable NI margin for the study. This change is reflected in this final SAP.

The European Medical Agency (EMA) has requested percent negative urine samples as the primary endpoint and retention rate as key secondary endpoint. These requests are addressed in a separate SAP for EMA submission. The variables related to the percentage of urine sample negative (EMA specific variables) are removed from Version 1.01 that is for FDA submission.

4.0 STUDY DESCRIPTION

4.1 STUDY OBJECTIVES

The primary objective of the study is to demonstrate non-inferiority of the CAM2038 buprenorphine (BPN) treatment arm as compared to the sublingual (SL) BPN treatment arm in treating adult outpatients with opioid use disorder, as measured by the primary efficacy measure of response rate (RR).

The secondary objectives of the study are:

- To evaluate the efficacy of CAM2038 compared to SL BPN in adult outpatients with opioid use disorder, as measured by cumulative distribution function of percent negative urines (supported by self-reported opioid use results) between Weeks 5 and 24.
- To evaluate the efficacy of CAM2038 compared to SL BPN in adult outpatients with opioid use disorder, as measured by the secondary efficacy measure of time to sustained abstinence from illicit opioid use.
- To evaluate the efficacy of CAM2038 compared to SL BPN in adult outpatients with opioid use disorder, as measured by the secondary efficacy measure retention rate.
- To evaluate the efficacy of CAM2038 compared to SL BPN in adult outpatients with opioid use disorder, as measured by the exploratory efficacy measures.

- To evaluate the safety of CAM2038 in adult outpatients with opioid use disorder.

4.2 STUDY TREATMENTS

In this double-blind and double-dummy study, subjects will be randomized to one of two treatment groups in a 1:1 ratio:

Treatment Group 1: SL BPN tablets + placebo subcutaneous (SC) injections

Treatment Group 2: CAM2038 SC injections + SL placebo tablets

4.3 STUDY DESIGN

This is a randomized, double-blind, double-dummy, active-controlled, parallel group multi-center trial, designed to evaluate the non-inferiority of CAM2038 compared to an existing standard of care (SL BPN) in initiation and maintenance treatment with BPN. The trial will involve 4 phases: Screening, Phase 1 (weekly visits), Phase 2 (monthly visits), and Follow-up.

Following Screening and confirmation of eligibility, subjects will be randomized to one of two treatment groups in a 1:1 ratio:

- Group 1: SL BPN tablets + placebo SC injections
- Group 2: CAM2038 SC injections + SL placebo tablets

Following randomization, subjects will undergo initiation of BPN treatment with either SL BPN or SC CAM2038 q1w, and participate in weekly visits for 12 weeks (Phase 1). After Week 12, subjects will be transitioned to Phase 2 with monthly visits. During Phase 2, subjects in Group 1 will continue treatment with monthly dispensing of daily SL BPN treatment and monthly placebo SC injections, and subjects in Group 2 (receiving CAM2038 q1w) will be transferred to monthly injections of CAM2038 q4w and monthly dispensing of daily SL placebo. Subjects will participate in 6 visits during the 12 weeks of Phase 2; 3 scheduled monthly visits and 3 random urine toxicology visits. At each random urine toxicology visit, subject's self-reported illicit use will be collected. After Phase 2, subjects will be followed-up for 4 weeks.

A total of 18 opioid urine toxicology samples will be collected during Phase 1 and Phase 2 of the trial, whereof 12 samples will be collected at the scheduled weekly visits during Phase 1. A total of 6 opioid urine toxicology samples will be collected during the 12 weeks of Phase 2 (3 at the scheduled monthly visits and 3 at random urine toxicology visits). A self-report of drug use will accompany every urine toxicology test.

Subjects who complete the 24 weeks of treatment (i.e., Phase 1 and Phase 2) will be transitioned to standard of care (e.g., SL BPN) and be followed up for 4 weeks.

All subjects will be blinded to their treatment group assignment, as will all trial staff with the exception of the clinician(s)/staff performing the SC injections and designated personnel who will be responsible for drug accountability (i.e., counting the active and placebo SL BPN returned tablets).

To ensure adequate enrollment and address potential inconvenience to subjects, all subjects (regardless of randomized group) will receive appropriate compensation for time and travel expenses related to attendance at trial visits. All costs of study related medications and counseling will also be covered. Investigators will be instructed to use manual-guided psychosocial counseling for trial subjects throughout the trial period.

4.4 RANDOMIZATION AND BLINDING

Randomization will be used to avoid bias in the assignment of subjects to treatment sequences, to increase the likelihood that known and unknown subject attributes (e.g., demographics, baseline characteristics) are evenly balanced across treatment groups, and to enhance the validity of statistical comparisons across treatment groups.

Subjects who have provided written informed consent will be assigned a unique number in the screening process. This number will be used to identify the subject throughout the study.

Subjects who have met the eligibility criteria (outlined in Section 8 of the clinical trial protocol) will be randomized to one of the 2 treatment groups in a 1:1 ratio (Treatment Group 1: SL BPN tablets + placebo SC injections or Treatment Group 2: CAM2038 SC injections + SL placebo tablets). Due to the size of the study, it is expected that subjects will be balanced for various other baseline factors, including age.

Once any subject number or randomization number is assigned, it cannot be reassigned to any other subject. This study will use central randomization, as described in Section 10.2 of the protocol.

In order to reduce the potential for bias in the study, treatment group assignments will be double-blinded. The subject, investigational site personnel, Sponsor, and Sponsor designees directly involved in the conduct and/or monitoring of this study will not be aware of the treatment group assignments. Sublingual BPN tablets used during the study will have a nearly-matching placebo.

Under normal circumstances, the blind will not be broken until all participants have completed treatment. In case of emergency, and only if the information is required by the Investigator to ensure subject's safety in managing a medical condition, the treatment may be unblinded at the site by using a code break module. The code break module will be provided by the Sponsor or designee. If possible, the Investigator should contact the Sponsor prior to unblinding and after any actions have been taken. Whenever a treatment sequence is prematurely unblinded, the reason, date and time of the unblinding, and the individual who broke the blind must be documented. Individual code breaks will result in withdrawal of the participant from the study.

5.0 ANALYSIS POPULATIONS

5.1 SAFETY POPULATION

The safety population will include all subjects who have any dose of SL BPN/placebo or SC CAM2038/placebo injection. Analyses based on this population will group subjects according to the treatment they actually received regardless of the treatment they were randomized to receive. All safety analyses will use the safety population.

5.2 INTENT-TO-TREAT POPULATION

The Intent-to-Treat (ITT) population will consist of all randomized subjects. The primary efficacy analyses will be based on the ITT population.

5.3 MODIFIED INTENT-TO-TREAT POPULATION

The modified Intent-to-Treat (mITT) population will consist of all randomized subjects who received any SL BPN/placebo or SC CAM2038/placebo injection. It is expected that the ITT and mITT population will be nearly identical. The results for the mITT population will not be presented if the two populations are differed by less than five (5) subjects as in this case the conclusions based on the two populations should be identical.

5.4 PER PROTOCOL POPULATION

The Per Protocol population will include all subjects in the ITT population with no major protocol violations. Major protocol violation criteria will be established prior to the data base lock. Protocol deviations will be presented in the clinical study report. Efficacy analyses may also be performed based on the per protocol population.

6.0 GENERAL CONVENTIONS

Unless otherwise stated, all analyses will be performed using SAS Version 9.2 or higher and all hypothesis tests will be conducted at a two-sided significance level of 0.05. P-values will be presented with 3 decimals and p-values that are less than 0.001 will be presented as <0.001.

Continuous (non survival related) data will be summarized using descriptive statistics: number of observations (n), mean, standard deviation (SD), median, minimum, and maximum. Frequencies and percentages will be used to summarize categorical (discrete) data. Presentations of categorical data will generally suppress percentages for items where the count is zero in order to draw attention to the nonzero counts. In general, mean, standard deviation, median, minimum, maximum, and percentages will be presented with one decimal.

Unless otherwise stated, confidence intervals, when presented, will be constructed at the two-sided 95% level. For binomial variables, the 95% confidence intervals will be constructed using the normal approximation without continuity correction.

Data listings will present all data collected on case report forms (CRFs) by study drug, center, and subject number. Unless otherwise stated data will be presented by treatment and overall.

6.1 DEFINITION OF BASELINE

Unless otherwise stated, the last observed measurement prior to or on the date of randomization will be considered the baseline measurement. If multiple observations are made during baseline, the baseline will be defined as average of the observations obtained during the baseline phase.

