7.1.2. Phase 1 (Weekly Visits)

Week 1 (Initiation of Treatment):

Eligible subjects will be initiated on BPN treatment, during which time they will attend trial visits at the site as needed based on their withdrawal symptoms. Prior to Day 1, subjects will be instructed to arrive at their Day 1 visit in a state of mild withdrawal, to avoid precipitated withdrawal with BPN.

A flow chart summarizing induction procedures is provided in Figure 4.

Day 1: On Day 1, after confirmation that subjects are in at least mild state of withdrawal, subjects will have an ECG performed as well as have their vitals taken. Subjects will then receive a test dose of unblinded 4 mg SL BPN film under observation prior to randomization to confirm tolerability by assessing signs and symptoms of precipitated withdrawal as measured by COWS.

One (1) hour, after tolerability has been confirmed and eligibility criteria have been re-checked, subjects will be randomized to one of two groups in a 1:1 ratio:

- Group 1 (SL BPN): Daily SL BPN + placebo SC injections
- Group 2 (CAM2038): CAM2038 SC BPN injections + daily SL placebo

After randomization, subjects will receive the following, while on site:

- A blinded dose of 4 mg SL tablets (active or placebo) will be administered under observation. Thus, the total Day 1 SL BPN dose is 8 mg (4 mg unblinded BPN film + 4 mg blinded BPN tablets) for Group 1 and 4 mg (4 mg unblinded BPN film) for Group 2.
- A single CAM2038 q1w (once-weekly) 16 mg SC injection (0.32 mL of active or placebo) will be administered.
- After receiving the first dose of study medications, the ECG and vitals will be repeated.
- If withdrawal symptoms are still not relieved after the second SL dose on Day 1, symptomatic relief with non-opioid medications should be provided.
- Subjects will be instructed to return to the clinic on Day 2 for observation and Day 2 dosing.

Day 2 and Day 3: All subjects will return to the clinic only on Day 2 for an additional observed dosing of SL BPN/Placebo to ensure continued tolerability. All subjects will receive 16 mg SL BPN/Placebo (two 8mg SL BPN or placebo tablets).

Administration of Day 2 SL BPN/Placebo dose will be observed in the clinic.

Subjects will also be provided with Day 3 take-home dose (two 8 mg SL BPN/Placebo tablets per day).

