10. TRIAL PROCEDURES AND ASSESSMENTS

All trial assessments will be performed at the visits and time points outlined in the Schedule of Assessments ([Table 3](#) and [Table 4](#)); the following sections outline the details and procedures associated with the assessments. Additional details on the assessments, including copies of questionnaires, logs, manuals, and information sheets are provided in the Trial MOP.

Table 3 Schedule of Assessments: Screening and Phase 1 (Weekly Visits)

	Trial Period/Phase:	Screening	Phase 1 (Weekly Visits)							
	Month:	-1	M1				M1-3			
	Week:	-3 to -1	W1				W2-W11		W12	
	Day:	-21 to -1	D1 ^a	D2	D3	D4	D5-7	D8	Weekly ^b	-
Informed Consent ^c	X									
Eligibility Criteria Review ^d	X	X								
Demographic Data and Psychosocial History	X									
Medical and Medication History/Substance Abuse and Treatment History (questionnaires)	X									
DSM-V	X									
Physical Examination ^e	X									
Weight, BMI	X	X							X	
Height	X									
Vital Signs ^f	X	X ^g				X		X	Weekly	X
ECG	X	X ^g						X	Weekly	X
Biochemistry, Hematology, Urinalysis and Coagulation Profile	X	X								X
Pregnancy Test ^h	X	X						X	Weekly	X
Hepatitis B/C, HIV ⁱ	X									
Injection Site Examination		X	X			X	(X)	X	Weekly	X

^a Subjects will be randomized to 1 of 2 treatment groups (SL BPN or CAM2038) after confirmation of eligibility ≥ 1 hour following a 4 mg SL BPN test dose.

^b A window of ± 2 days will be allowed for weekly visits during Weeks 2 to 12, in addition to Week 13.

^c Subjects must voluntarily provide written informed consent prior to any trial-related procedures being performed.

^d Prior to randomization on Day 1, a review of the eligibility criteria will be made

^e A complete physical exam of all major body systems will be performed at the Screening visit.

^f Includes temperature, blood pressure, pulse rate, respiration rate.

^g Vital signs and ECG will be measured at approximately 15-30 minutes before the test dose and approximately 15-30 minutes after the CAM2038/SL BPN dose on Day 1 and approximately 15-30 minutes pre-dose at the other visits as indicated in the table (or during the visit if no dose is given).

^h A serum pregnancy test will be performed at Screening. An “in-office” urine pregnancy test will be required on Day 1 PRIOR to randomization and test dose administration as well weekly thereafter (for women of childbearing potential).

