ⁱ It is the Investigator’s responsibility to understand and comply with all laws and regulations that apply to HIV, Hepatitis B, and Hepatitis C and testing of blood. Hepatitis B/C and HIV testing is required unless a site’s IRB prohibits such testing.

Trial Period/Phase:	Screening	Phase 1 (Weekly Visits)							
	Month:	-1	M1				M1-3		
	Week:	-3 to -1	W1				W2-W11		W12
	Day:	-21 to -1	D1 ^a	D2	D3	D4	D5-7	D8	Weekly ^b
Dispense Treatment Identification Card		X							
Urine Toxicology	X	X					X	Weekly	X
Illicit Drug Use Self-Report	X	X					X	Weekly	X
SOWS, COWS, VAS ^j	X	X	X		X	(X)	X	Weekly	X
C-SSRS ^k	X	X	X		X	(X)	X	Weekly	X
Measurement of Morning Desire to Use/Need to Use							X	Weekly	X
SL BPN or SL placebo dispensing		X	X		X	(X)	X	Weekly	X
SL BPN or SL placebo administration ^l		X	X	X	X	Daily	X	Daily	X
CAM2038 q1w or placebo SC injection ^m		X			X	(X)	X	Weekly	X
Psychosocial Counseling		X					X	Weekly	X
Adverse Events ⁿ	X	X	X		X	(X)	X	Weekly	X
Concomitant Medications/Procedures	X	X	X		X	(X)	X	Weekly	X
On-site visits	X	X	X		X	(X)	X	Weekly	X

Abbreviations: BMI=body mass index; BPN=buprenorphine; COWS=Clinical Opiate Withdrawal Scale; C-SSRS=Columbia Suicide Severity Rating Scale; D=day; DSM-V= Diagnostic and Statistical Manual of Mental Disorders – Fifth Edition; ECG=electrocardiogram; HIV=human immunodeficiency virus; M=month; SC=subcutaneous; SL=sublingual; SOWS=Subjective Opiate Withdrawal Scale; VAS=visual analogue scale; W=week (X) indicates as needed based on the individual subject.

^j SOWS/COWS/VAS will be completed each time the subject visits the clinic, as needed based on titration and dosage adjustment. On Day 1, COWS, SOWS and VAS will be completed before the test dose is administered (baseline). COWS will also be completed after the test dose on Day 1 to evaluate tolerability, and on Day 2.

^k Screening version at Visit 1 (Screening), Since Last Visit version at all subsequent visits.

^l Not to exceed 24 mg SL BPN (or placebo) per day, this administration will be done at home.

^m Not to exceed 32 mg CAM2038 q1w (or placebo) per week.

ⁿ Any spontaneously reported adverse event will be recorded after the subject signs the informed consent form. In addition, adverse events will be elicited using a non-leading question each time the subject visits the clinic.

Table 4 Schedule of Assessments: Phase 2 (Monthly Visits) and Follow-up

Trial Period/Phase:	Phase 2 (Monthly Visits)						Follow-up			
	Month:	M4		M5		M6		M7		

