10.4.4. Vital Signs

Vital signs will consist of temperature, blood pressure (systolic and diastolic blood pressure, mmHg), pulse rate (beats per minute), and respiratory rate (breaths/min) collected while sitting, following a rest period of at least 3 minutes, at the time points indicated in Table 3 and Table 4. On Day 1, vital signs will be measured approximately 15-30 minutes before the subjects receive their SL BPN test dose and approximately 15-30 minutes after they have received their doses of blinded CAM2038 q1w/SL BPN (placebo or active). At Week 13, vital signs will be measured approximately 15-30 minutes pre-dose and approximately 15-30 minutes post-dose. At the other visits, vital signs will be measured approximately 15-30 minutes pre-dose (or during the visit if no dose is given). Clinically significant values will be recorded as AEs.

10.4.5. 12-Lead Electrocardiogram (ECG)

12-Lead ECGs will be performed after the subject has been resting in a recumbent/supine position for at least 3 minutes, at the time points indicated in Table 3 and Table 4. On Day 1, an ECG will be performed approximately 15-30 minutes before the subjects receive their SL BPN test dose and approximately 15-30 minutes after they have received their doses of blinded CAM2038 q1w/SL BPN (placebo or active). At Week 13, ECGs will be performed approximately 15-30 minutes pre-dose and approximately 15-30 minutes post-dose. At the other visits, ECGs will be performed approximately 15-30 minutes pre-dose (or during the visit if no dose is given). The ECG variables will include ventricular heart rate and the PR, QRS, QT, QTcB and QTcF intervals. The ECGs will be signed and dated by a medically-qualified individual to confirm review of the ECG and verify whether any abnormalities are clinically significant. In general, abnormal, clinically significant ECGs are expected to be associated with an item recorded in medical history or with an AE.

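### The SAP's date-based baseline rule makes the Day 1 post-dose ECG and vital signs the baseline, and it conflicts with the averaging rule that follows it

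*SAP*

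**What the plan says.** SAP 6.1 gives two rules in succession. The first is "the last observed measurement prior to or on the date of randomization will be considered the baseline measurement". The second is "If multiple observations are made during baseline, the baseline will be defined as average of the observations obtained during the baseline phase". The section yields to anything stated elsewhere, but it sets no clock time, sets no pre-dose condition and does not define the baseline phase.

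Protocol Table 3 places randomization, the test dose and the first blinded dose on the same day. Footnote d reads "Prior to randomization on Day 1, a review of the eligibility criteria will be made". Under footnote g, vital signs and ECG are "measured at approximately 15-30 minutes before the test dose and approximately 15-30 minutes after the CAM2038/SL BPN dose on Day 1". Protocol 7.1.2 agrees: "After receiving the first dose of study medications, the ECG and vitals will be repeated". For the withdrawal and craving scales, footnote j labels the scores taken before the test dose as baseline and adds "COWS will also be completed after the test dose on Day 1 to evaluate tolerability".

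SAP 10.4 (vital signs) and 10.6 (ECG) summarize change without a baseline rule of their own. SAP 10.6 also sorts QT, QTcB and QTcF changes into <30, 30 to <60 and >=60 msec. Only laboratory data have a separate rule (SAP 10.3). SAP 9.3.10 analyzes change in COWS by ANCOVA with baseline as covariate and points to Table 3 for the measurement schedule.

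**The concern.** A baseline should precede treatment. Here the calendar-date cut-off admits readings taken after the test dose and, for ECG and vital signs, after the randomized drug. The repeat reading exists to look at the subject just after dosing. If it becomes the baseline, the effect it was meant to show is subtracted from every later change. The QT/QTc change categories have fixed cut-offs, so even a small displacement can move a subject across one.

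The second rule makes matters less certain. Last value and average are different quantities, a programmer cannot apply both, and the documents do not say which prevails.

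**Working it through.** No figure in the plan depends on the baseline rule, so there is none to reproduce. The check applies SAP 6.1 to the Day 1 schedule.

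**Order of events on Day 1** (Protocol 7.1.2, 10.4.4, 10.4.5; Table 3 footnotes a, g, j):

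1. ECG, vital signs, COWS, SOWS and VAS
2. 4 mg open-label test dose
3. COWS again
4. Randomization, at least 1 hour after the test dose
5. Blinded SL tablets and SC injection
6. ECG and vital signs again, 15-30 minutes later

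**What each rule selects** (Table 3 also schedules all of these measures at Screening, up to 21 days earlier):

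| Measure | Readings up to the end of Day 1 | Last value | Average |
|---|---|---|---|
| ECG, vital signs | Screening; pre-test-dose; post-blinded-dose | Post-blinded-dose | May include the post-blinded-dose reading |
| COWS | Screening; pre-test-dose; post-test-dose | Post-test-dose | May include the post-test-dose score |
| SOWS, VAS | Screening; pre-test-dose | Pre-test-dose (harmless) | May blend in Screening |

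**Displacement.** Let the pre-test-dose value be b, the later Day 1 value b + d, the Screening value b + e, and the follow-up value y. The change from a pre-dose baseline is C = y - b.

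- Last value: y - (b + d) = C - d
- Average of the two Day 1 readings: C - d/2
- Average of those two and one Screening reading: C - (d + e)/3, so d enters as d/3 and a Screening difference is added
- At the Day 1 post-dose reading itself, C = d. The recorded change is d - d = 0 by construction under last value, and d - d/2 = d/2 under the two-reading average.

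**Illustration for QTcF.** The documents give no d, so these shifts are assumed. The change from a pre-dose baseline is +60 msec and e = 0.

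| d (msec) | Last (60 - d) | Average of two (60 - d/2) | Average of three (60 - d/3) |
|---|---|---|---|
| 2 | 58 | 59 | 59.3 |
| 5 | 55 | 57.5 | 58.3 |
| 10 | 50 | 55 | 56.7 |
| 15 | 45 | 52.5 | 55 |

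Every entry leaves the >=60 category. With the opposite sign the error reverses: for an assumed change of +55 and d = -5, last value gives 55 + 5 = 60, which enters it.

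**Between arms.** With mean shifts dT and dC, the difference in mean change is displaced by -(dT - dC) under last value and by half that under the two-reading average. Assumed differences of 2, 5 or 10 units give -2, -5 or -10, and -1, -2.5 or -5.

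**COWS.** The algebra is the same, with d now the effect of the open-label test dose. For an assumed change of -10 and d of -1, -2, -4 or -6, last value records -9, -8, -6 or -4, and the two-reading average -9.5, -9, -8 or -7. The post-test-dose score precedes randomization. For any baseline c, an ANCOVA of y - c on treatment and c gives the same treatment effect as an ANCOVA of y on treatment and c. Using a different pre-randomization score as c can change precision but leaves the comparison valid.

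**The case against.** **COWS is largely handled.** SAP 6.1 gives way to statements elsewhere, and SAP 9.3.10 points to Table 3, whose footnote j names the pre-test-dose score as baseline. A reader might infer that the SAP flatly contradicts the protocol, but the documents can be read together without contradiction. What stands is that the pointer concerns when scores are measured and the SAP never restates the label, so the date rule and the footnote give different answers until it does. Footnote g, for ECG and vital signs, labels neither reading as baseline, so this answer does not extend to them.

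**The baseline phase may mean pre-dose.** Protocol 7.1 places the baseline urine sample before the first CAM2038 q1w dose, and footnote j places the scales before the test dose. On that reading no post-dose value is averaged in. This is plausible, which is why the averaging rule can only be said to possibly include them. But the term is undefined, the preceding sentence takes in the whole randomization date, and a pre-dose average could still blend in Screening.

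**Direction and arm difference.** A reader might infer that early QTc effects are understated, or that the safety comparison is biased by arm. The documents support neither. The repeat reading comes 15-30 minutes after the blinded dose. Protocol 5.1.3 expects clinically relevant CAM2038 levels about 2-4 hours after injection, and both arms have already had the same 4 mg film. Total Day 1 SL buprenorphine does differ (8 mg in Group 1, 4 mg in Group 2), so a differential shift is possible, but its size and sign are not given.

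**Scope.** The affected ECG and vital sign summaries are descriptive, SAP 10.0 calls any formal safety comparison post hoc, and the absolute QT/QTc categories use no baseline. All of this stands and limits the consequence.

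**Conclusion.** Wrong as written, with a limited reach. Taken literally, the first rule in SAP 6.1 makes a post-treatment reading the baseline for ECG and vital signs in every subject who has the scheduled Day 1 repeat. The second rule conflicts with the first and may mix that reading in.

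The displacement is d under last value, d/2 if only the two Day 1 readings are averaged, and d/3 (plus a Screening term) if one Screening reading is included. This is algebra. The msec and COWS figures are illustrations on assumed shifts and do not predict what the trial will show. No claim about the direction of error in QTc, or about bias between arms, can be drawn from the documents.

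For COWS, an exploratory measure, the defect is a label that the SAP fails to carry over. It bears on within-arm change and the covariate and leaves the arm comparison valid. The primary responder rate and the secondary endpoints (CDF of negative samples, time to sustained abstinence, retention) use no baseline value and are unaffected.

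**What to change.** Replace the two rules in SAP 6.1 with one: *Baseline is the last non-missing value obtained before the Day 1 test dose, by date and time.* Delete the averaging sentence. State that the rule governs COWS in SAP 9.3.10, where it agrees with protocol Table 3 footnote j, vital signs in 10.4, and ECG in 10.6, including the QT/QTc change categories. If the Day 1 pre-dose value is missing, the rule falls back on Screening without further text.

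Summarize the later Day 1 readings (ECG and vital signs after the blinded dose, COWS after the test dose) as separate post-dose time points, so that they show a change rather than a built-in zero.

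The cost is one SAP sentence and a pre-dose flag in programming, based on clock time. No new data are needed, because the schedule already ties these readings to dosing. The change belongs in the SAP before database lock and unblinding.
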